We describe all study measures in detail in the study design and procedures sections below and they appear in our appendices. Below is a brief summary of assessments. Purchasing Survey: After obtaining permission from caregivers, a survey will be administered to students after they have made a food or beverage purchase at a school store. The survey will assess participants nutrition knowledge and label awareness, recall, and use, and trust in label information. Frequency of school store visits and sociodemographic characteristics (e.g., age, sex, race/ethnicity, grade level, and height and weight) will also be assessed (see Appendix B for survey). Beverage Frequency Questionnaire: Participants will also complete a beverage frequency questionnaire to assess their consumption of different types of beverages. This questionnaire will be based on the BEVQ-15, a survey instrument that has been validated as an effective tool used to capture changes in beverage consumption. (1-4) (see Appendix E for BEVQ-15). For each beverage category, the questionnaire assesses frequency of consumption and volume typically consumed. (see Appendix D for adapted questionnaire).

Group Modifications

Describe necessary changes that will or have been made to the study instruments for different groups.

None of the survey questionnaires will differ across randomly assigned groups. Regarding the schools that will be enrolled in the study, pairs of matched private/public schools will be randomized to 1 of 3 labeling conditions

Method for Assigning Subjects to Groups

Describe how subjects will be randomized to groups.

Individual participants will not be randomly assigned to groups. Instead, randomization will occur at the school level. Nine schools will be participating in this research and randomization will be stratified based on whether a school is public (n = 6) or private (n = 3). The Penn research team will use a random number generator to randomize schools to one of three labeling conditions, and the Guatemala team will implement the labels based on the randomization assignment.

Administration of Surveys and/or Process

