As co-principal investigators, Drs. [name] and [name] will meet by Skype conference calls weekly to assess the interim results and the coordination of any modifications to the protocol. In the event that any unanticipated problems involving risk to participants or others occurs, the co-principal investigators will communicate immediately to effectively address and manage these risks. Throughout the study a reliable and effective channel of communication will be upheld between both teams at INCAN and The University of Pennsylvania. There will be data and safety monitoring meetings every 6 months to more specifically assess the data quality, participant recruitment, accrual and retention, participant risk versus benefit, and study outcomes. The research team will also correspond by email and telephone as needed. Only the researchers involved in these studies and those responsible for research oversight will have access to the identifiable information provided. In addition, the data collected as part of this study will not contain identifying information, which will therefore pose minimal risk to its participants.

The following documents are currently attached to this item:

There are no documents attached for this item.

Protocol

Abstract

Guatemala is a lower middle income country struggling with the double-burden of disease (malnutrition and obesity coexisting). Consumption of sugary drinks is strongly associated with obesity and related health problems. Food labeling has become a popular policy approach to address high levels of sugary drink intake. Some countries are interested in placing health warning labels on sugary drinks, but there are no real-world studies testing the effects of such labels. The aim of the proposed research is to test the effect of repeated exposure to warning labels on mean fluid ounces of sugary drinks purchased by adolescents in Guatemala. We define a sugary drink as any non-alcoholic beverage that lists any form of caloric sugar-based sweetener as an ingredient (this would not include 100% juice). We will enroll nine schools in the study (three private and six public). Each group of matched private/public schools will be randomized to 1 of 3 labeling conditions. In this six-week study, we will collect sales data during two weeks without labels, two weeks when labels are displayed, and two weeks after labels have been removed. We will also conduct surveys with 1500 students.

Objectives**Overall objectives**

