have shopped at one of the participating stores will qualify to participate. We will use the communication channel each school prefers (e.g., e-mail, printed letters sent home with students) to send permission letters to caregivers (see Appendix A). The letters will explain that their children may be asked to complete a short survey after making a purchase at the school store. Caregivers who wish to refuse participation can call a number provided in the permission letter. All students whose caregivers did not withdraw will be eligible to participate in the survey. Permission letters will be sent two weeks before data collection. Adolescents who have made a purchase from the school store will be asked if they want to complete a short survey; verbal assent must be obtained prior to enrollment (see Appendix C for oral consent script). School Store Setting: Nine schools will be participating in this research and randomization will be stratified based on whether a school is public (n = 6) or private (n = 3). The Penn research team will use a random number generator to randomize schools and the Guatemala team will implement the labels based on the randomization assignment. Each pair of matched private/public schools will be randomized to 1 of 3 labeling conditions: 1) calorie label (control); 2) text warning labels; or 3) graphic warning labels displaying amounts of sugar (see Appendix F). The warning label language will be translated into Spanish before the labels are implemented in the school stores. In this six-week study, we will receive purchasing data from the schools during two weeks without labels, two weeks when labels are displayed, and two weeks after labels have been removed. Warning Label Survey: During the intervention weeks, we will survey approximately 1500 adolescents after they have made a purchase at the school store. We will stratify recruitment to ensure approximately half of the 1500 surveyed students (n=750) are enrolled in public school and half (n=750) are enrolled in private school. Adolescents will be asked if they want to participate in a short, 5-10 minute survey. They will be offered a small prize (e.g., school supplies like pens or pencils) as a token of appreciation. The survey will include constructs that map onto our conceptual model of label effects, such as nutritional knowledge, label awareness, and trust of information on nutritional labels (see Appendix B for survey questions). We will also administer a beverage intake questionnaire (see Appendix D). This questionnaire has been validated among children and adolescents (42,43) Demographic Information: During the survey, we will ask participants to provide basic demographic information including age, sex, race/ethnicity, grade level, and height and weight (see Appendix B for demographic questions). Sales Data: We will collect sales data by setting up a point of sale system in each school store. This system will allow us to collect sales data from each store that will include a row for each purchase made at the school store, including the date of the transaction and the type of food or beverage sold (e.g., diet soda, lemonade) along with the item brand, size, quantity, and price. We will also record the presence and type of food/beverage marketing in the store.

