include 100% juice). Frequencies and percentages will be used to describe categorical variables such as percent of students purchasing a sugary drink. Medians and interquartile ranges will be reported for continuous variables that exhibit skewness. Data will be descriptively summarized overall and by labeling strategy. All outcomes will be analyzed at the purchase level. The mean volume of sugary drinks at each two-week period will be modeled among the calorie label, text label, and graphic label arms by a linear regression model including intervention arm, two-week period, interactions of period and intervention arm and type of school (private or public) as independent variables. We will conduct exploratory analyses to examine whether usual frequency of sugary drink intake (high versus low) and biological sex moderate label effects. Examining only aggregate sales data could lead to incorrect inferences. Therefore, complementary individual-level survey data on purchases will also be collected. This aggregate/individual-level data combination will improve inferences about label effects. Although stratification by school type guarantees this variable will be balanced across our intervention arms, we are including it as a covariate in the model because it will enhance the precision of estimating intervention effects, as it explains variability in the outcome. The effectiveness of the interventions will be tested by evaluating the null hypothesis that the coefficients of the interactions of period and intervention are 0, indicating no change in the difference in volume of sugary beverages purchased across intervention arms from baseline. To account for clustering of purchases within schools, test statistics will be corrected using the variance inflation factor (VIF) as determined by the estimated intraclass correlation coefficient (ICC) for within school correlation. Primary and secondary outcomes in the calorie, text-based warning label, and graphic warning label arms will each be compared to one another. A Bonferroni-holm correction will be applied to control for multiple comparisons. We do not expect substantial missing data due to the point-of-sale technology we are using. The primary analysis will examine changes in labeled (sugary) and non-labeled beverages. Secondary analyses will examine changes for the following specific beverage categories: sugar-sweetened cola, sugar-sweetened sports drinks, sugar-sweetened lemonades/iced teas/juices, artificially-sweetened drinks (e.g., Diet Coke), milk, 100% fruit juice, unsweetened coffee/tea, and bottled water. For the survey data, we will conduct similar linear regression analyses to compare total mean kcals purchased among intervention arms.

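### The protocol's nine-school purchase-level model has no school term, so an uneven shift in purchase mix within an arm can move the estimated label effect although no school changed

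*Protocol*

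**What the plan says.** The point concerns the protocol's Analysis Plan for the sales data.

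- **Unit.** "All outcomes will be analyzed at the purchase level". A school's weight in its arm's mean is therefore its number of purchases in that period.
- **Model.** Mean volume per two-week period is estimated "by a linear regression model including intervention arm, two-week period, interactions of period and intervention arm and type of school (private or public"). No school fixed or random effect is named.
- **Test.** The null hypothesis is that "the coefficients of the interactions of period and intervention are 0, indicating no change in the difference in volume of sugary beverages purchased" across arms from baseline.
- **Clustering.** "test statistics will be corrected using the variance inflation factor (VIF) as determined by the estimated intraclass correlation coefficient (ICC"). This is the only provision for individual schools.
- **Design.** There are nine schools, and "randomization will be stratified based on whether a school is public (n = 6) or private (n = 3"). The arms are "1) calorie label (control); 2) text warning labels; or 3) graphic warning labels displaying amounts of sugar". The periods are "two weeks without labels, two weeks when labels are displayed, and two weeks after labels have been removed". An even split of each stratum gives two public schools and one private school per arm.
- **Data.** The point-of-sale system will "collect sales data from each store that will include a row for each purchase made at the school store", so the school is known for every row.

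The SAP describes something different: a difference-in-differences model whose primary analysis uses one treatment school and one control school.

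**The concern.** The two-week baseline allows each school to serve as its own control. The planned model does not use it that way. It compares purchase-weighted arm means, adjusted for school type. School type separates private from public, but it cannot tell an arm's two public schools apart.

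Suppose those two schools differ in ounces per purchase. Suppose also that one of them trades fewer days, loses till records or simply has less traffic in the label weeks. Its weight falls and the arm mean moves towards the other school. If the other arms do not shift in the same way, the arm-by-period coefficient records this as a label effect. At stake are the point estimate of the primary effect and the centre of its interval. A correction to the standard error alters neither.

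**Working it through.** **Inputs.** From the protocol: three arms, three periods, nine schools (six public, three private), purchase-level weighting and the model terms above. Two public schools and one private school per arm follows if strata are split evenly. The documents give no school means, purchase counts, store closures or intraclass correlation, so those below are assumptions. The protocol states no figure on this point to reproduce; its one power figure, for the 1500-student survey, is not an input.

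**Method.** Every school's mean is held constant over time, so the true label effect is zero. Two models are fitted by purchase-weighted least squares to the 27 school-by-period means, without noise: (a) the protocol's terms; (b) nine school indicators in place of the arm and school-type main effects, with period and arm-by-period kept.

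**1. Shift in the split between two public schools.** One arm's public schools differ by a gap *g*, all other schools are at 6 oz, and there are 2,000 purchases per school-period. In the label period, a fraction *s* of that arm's public purchases moves from the higher school to the lower one. Public purchases are 2/3 of the arm, so

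distortion = -(2/3) × *g* × *s*.

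| Gap *g* | *s* = 0.05 | *s* = 0.10 | *s* = 0.20 |
|---|---|---|---|
| 1 oz | -0.033 | -0.067 | -0.133 |
| 2 oz | -0.067 | -0.133 | -0.267 |
| 4 oz | -0.133 | -0.267 | -0.533 |

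Model (a) returns these values in oz. Model (b) returns 0 in every cell.

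**2. Lost trading days.** The higher school loses a share of its label-period purchases. For a 4-oz gap (8 and 4 oz) and 3 of 10 days lost, the raw arm mean is

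(8 × 1,400 + 4 × 2,000 + 6 × 2,000) / 5,400 = 31,200 / 5,400 = 5.778 oz,

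a change of -0.222 oz. Model (a) gives -0.224, because the type term alters the weights slightly.

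| Gap | Days lost | Model (a) | Share of 6 oz | Model (b) |
|---|---|---|---|---|
| 1 oz | 1 of 10 | -0.017 | 0.3% | 0 |
| 2 oz | 1 of 10 | -0.035 | 0.6% | 0 |
| 4 oz | 3 of 10 | -0.224 | 3.7% | 0 |
| 4 oz | 5 of 10 | -0.404 | 6.7% | 0 |

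**3. Where the effect vanishes.**

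- If every school loses 30% of its purchases, model (a) gives 0.
- If all arms have the same gap and the same shift, model (a) gives 0.
- If one arm's private share rises from 1/3 to 1/2, with the same 3-oz private/public gap in all arms, the raw arm mean moves by -0.5 oz but model (a) gives 0, because the type term absorbs it.
- With that same share shift, but a 6-oz type gap in the shifting arm only, model (a) gives -0.329 oz and model (b) gives 0.

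**4. Effect on the test.** Purchases were simulated with no label effect, about 1,000 per school-period, and counts varying with a log-scale SD of 0.3 (2,000 runs per setting).

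| Intraclass correlation | Model (a), no correction | Model (a), planned correction | Model (b) |
|---|---|---|---|
| 0.01 | 10% | about 0% | 5% |
| 0.05 | 25% | about 0% | 5% |
| 0.10 | 39% | about 0% | 5% |

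The correction was taken as 1 + (m - 1) × ICC, with m the purchases per school. At m = 3,000 and ICC = 0.01 it is 1 + 2,999 × 0.01 = 31, so the test statistic is divided by about 5.6. For a contrast made largely within schools this is very conservative. The simulation gave schools no period-to-period variation of their own, so the 5% for model (b) does not justify using purchase-level residual error in practice.

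**5. Two remedies, two targets.** Let one arm's schools have 4,000, 1,000 and 1,000 purchases per period, with only the largest falling by 1 oz. School indicators on purchases give -4,000/6,000 = -0.67 oz. The unweighted mean of the three school changes is -1/3 = -0.33 oz. If the large school also loses half its label-period purchases, the indicator estimate becomes -0.55 oz. School indicators remove differences that are constant over time; when schools respond differently, the estimate still depends on purchase volumes.

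**The case against.** **The SAP.** Its primary analysis has one school per arm, so the treatment indicator is the school indicator and there is no within-arm mix to shift. This stands. A reader might infer that every planned primary analysis in the documents is affected; the SAP's is not. The exposure would return under the SAP's equation only if the third school were pooled into an arm.

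**Bias.** A reader might infer systematic bias. Shifts unrelated to arm have no preferred direction and add error that averages to zero over randomizations. Systematic bias needs shifts linked to arm, and nothing in the documents points to that. This stands.

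**Type I error.** A reader might infer false positives. The planned correction gave about 0% rejection in the simulation, so inflation is not shown. This stands, but the correction does not move a distorted estimate back.

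**School type is already in the model.** This is partly right. The type term absorbs a private/public shift when the type gap is the same in all arms. It cannot absorb a shift between two public schools, or a type gap that differs by arm.

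**Size.** The larger figures need two schools of the same type 4 oz apart on a 6-oz mean. The protocol expects similar demographics within school type and little missing point-of-sale data. Both make small values more plausible. Neither settles the matter, because similar demographics do not ensure similar purchases, and a closed store or changed traffic alters the weights without any missing record.

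**Conclusion.** The concern holds for the protocol's nine-school model, in limited form. With no school term, the arm-by-period estimate can move when no school has changed. Two conditions are needed: schools within an arm must differ in ounces per purchase in a way the common school-type term does not capture, and their purchase mix must shift differently from the other arms. The planned correction leaves that error in the estimate.

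Under the assumed inputs the distortion is about -0.02 to -0.03 oz for small gaps and small losses, -0.13 oz for a 2-oz gap with a 10-point shift, and -0.40 oz for a 4-oz gap with half the days lost. The sign reverses if the lower-volume school is the one that loses purchases. The algebra is certain; the practical size is not, because the documents give no school means or counts. A change to the plan is worth making because the error is avoidable at almost no cost.

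**What to change.** In the protocol's nine-school model:

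1. Replace the arm and school-type main effects by nine school indicators. Keep period and arm-by-period. Both replaced terms are fully absorbed by the school indicators.
2. Base the standard error on between-school variation in the nine school-level changes from baseline, not on purchase-level residuals or on the intraclass correlation left after the indicators. With three arms this leaves 9 - 3 = 6 degrees of freedom for each change.
3. State the target. Purchase-weighted school indicators estimate a per-purchase effect. Comparing unweighted school-level changes between arms estimates a per-school effect. Choose one in advance and report the other, if wanted, as a sensitivity analysis.
4. Report purchases and trading days by school and period, so that readers can see any shift in mix.

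The cost is wording in the analysis plan. No new data are needed, since sales are recorded by store. School differences that are constant over time cancel from the tested change, so the indicators give up nothing for that contrast. The SAP's two-school primary analysis needs no change on this account.

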
Study duration

We anticipate it will take the entirety of the six week data collection period to survey all 1500 adolescents. It will take 5-10 minutes for each participant to complete the survey. We aim to implement the warning labels in school stores by May 2018 and will complete the data collection by the end of June 2018.

Resources necessary for human research protection

Describe research staff and justify that the staff are adequate in number and qualifications to conduct the research. Describe how you will ensure that all staff assisting with the research are adequately informed about the protocol and their research related duties. Please allow adequate time for the researchers to conduct and complete the research. Please confirm that there are adequate facilities for the research.

Characteristics of the Study Population

Target population

To be eligible for the survey component of this project, participants must be: 1) Between 12-18 years or older; 2) Be a currently enrolled student at one of the enrolled schools 3) Have made a purchase at the school store.

Subjects enrolled by Penn Researchers

0

Subjects enrolled by Collaborating Researchers

1500

Accrual

The schools participating in this study will enable us to easily recruit students shopping at the school stores. With a sample size of 1500 (500 per labeling condition), this study is powered to detect small mean differences between the conditions. Specifically, if all three conditions differ by only .21 standard deviations, there is an 82% chance that we would find all differences to be significant.

Key inclusion criteria

To be eligible for the survey component of this project, participants must be: 1) Between 12-18 years or older; 2) Be a currently enrolled student at one of the enrolled schools 3) Have made a purchase at the school store.

Key exclusion criteria

Individuals not meeting the inclusion criteria above will be excluded. Those who will not or cannot give assent will also be excluded from the study. No one will be excluded on the basis of sex or race

Vulnerable Populations

Children Form

Pregnant women (if the study procedures may affect the condition of the pregnant woman or fetus) Form

Fetuses and/or Neonates Form

Prisoners Form

Other

None of the above populations are included in the research study

The following documents are currently attached to this item:

Vulnerable Populations (inclusionofchildren.doc)

Populations vulnerable to undue influence or coercion

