### **Description of data:**

The first is a longitudinal data set (at the school level) of store purchases from July – August 2019 obtained by trained research assistants in three schools located in Guatemala City. Data are daily purchases of food items and beverages by students. Sample is total purchases obtained from scanning products' barcodes or using an application (Square app) to assign unique codes to products without a barcode. Data include food purchases, brand, flavor, size, and quantity. Additionally, an inventory of beverages' brand, flavor, price, size (mL), serving size (mL) as reported in the Nutrition Facts Panel, calories (kcal), total fat (g), saturated fat (g), total carbohydrates (g), sugar (g), sodium (mg), protein (g), ingredients, total sugar, sodium, and protein per container (g).

The second dataset is an intercept survey conducted with students after they made a purchase at the school store. Data include total expenditure, number and type of items purchased (i.e., beverage, food, or non beverage/food item), perception of healthfulness of

specific beverages (i.e., water, fruit drink, soft drink, light soft drink), and the label awareness, recall, use, and trust. Usual SSB consumption, demographics, height, and weight are also included in the survey.

For our primary analysis, we will look only at the 2 schools which were randomly assigned to condition (one treatment and one control school).

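### The protocol's exploratory moderation analysis reduces usual sugary-drink intake to high versus low with no cut-point, although a graded measure can be derived from the questionnaire

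*Protocol*

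**What the plan says.** The Analysis Plan section of the protocol introduces the moderation work with "We will conduct exploratory analyses to examine whether" and names the two moderators: "usual frequency of sugary drink intake (high versus low) and biological sex moderate label effects". It defines neither high nor low, does not say why two groups are used, and offers no graded alternative.

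The protocol's summary of the Beverage Frequency Questionnaire describes what is collected: "For each beverage category, the questionnaire assesses frequency of consumption and volume typically consumed". The response options are in an appendix that is not among the documents.

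The SAP, under Description of data, confirms that the variable exists: "Usual SSB consumption, demographics, height, and weight are also included in the survey". Its aims, hypotheses, outcomes and statistical analysis contain no moderation analysis.

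No distribution is given for usual intake. The nearest statement is general: "Medians and interquartile ranges will be reported for continuous variables that exhibit skewness". The only power statement, in the protocol's Accrual section, concerns the comparison of label arms.

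**The concern.** A graded measurement is collected and then used only as two groups. This has two consequences.

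- **Lost information.** If the effect of the labels rises or falls steadily with usual intake, the split treats all students on one side of the cut as alike and those just either side of it as different. An interaction test built on the split is weaker than one built on the graded measure. Interaction tests are usually weak to begin with.
- **An open cut-point.** With high and low undefined, the threshold can be chosen after results are seen, and the finding may depend on where it falls. This applies whatever the distribution of intake.

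At stake is whether the exploratory analysis can detect a real gradient in label effect by usual intake, and whether a reported subgroup difference could be trusted. The trial's main comparisons are not at stake.

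**Working it through.** **1. The plan's own figure.** The Accrual section says: "With a sample size of 1500 (500 per labeling condition), this study is powered to detect small mean differences between the conditions", and that "if all three conditions differ by only .21 standard deviations, there is an 82% chance that we would find all differences to be significant". The Analysis Plan adds: "A Bonferroni-holm correction will be applied to control for multiple comparisons". Alpha and sidedness are not stated; 0.05 two-sided is assumed.

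- Standard error of a difference in SD units: √(2/500) = 0.0632. Ratio: 0.21/0.0632 = 3.32.
- At alpha 0.05/3 the critical value is 2.394, so power = Φ(3.32 − 2.394) = 82.3%.
- Simulating all three pairwise tests with arm means 0, 0.21 and 0.42 SD gives 82.5% under Holm.

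The stated 82% is reproduced, without clustering. It is a figure for arm differences. No corresponding figure exists for moderation, so the starting powers of 80% and 90% below are illustrative.

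**2. Information kept by a split.** Assume a linear gradient and the same intake distribution in each arm. The share of interaction information kept is then the squared correlation between intake and its high/low indicator. For a normal moderator with a proportion p below the cut:

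kept = φ(z_p)² / [p(1 − p)]

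- Median: 0.3989²/0.25 = 0.637 (that is, 2/π). Loss 36%.
- 30/70: kept 0.576. Loss 42%.
- 25/75: kept 0.539. Loss 46%.
- 20/80: kept 0.490. Loss 51%.

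At the median, which is the best single cut under normality, 1500 × 0.637 = 955: the full sample carries the interaction information of about 955 students.

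**3. Effect on power** for a single interaction contrast at two-sided 0.05, normal moderator, median cut (√0.637 = 0.798):

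- From 80%: (1.960 + 0.842) × 0.798 = 2.236; Φ(2.236 − 1.960) = 61%.
- From 90%: (1.960 + 1.282) × 0.798 = 2.587; Φ(2.587 − 1.960) = 73%.

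**4. Other shapes.** Loss with the gradient linear on the scale shown (non-normal shapes by simulation, 4 million draws each):

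| Assumed intake distribution | Median cut | Top 25% called high |
|---|---|---|
| Uniform | 25% | 44% |
| Normal | 36% | 46% |
| Gamma, shape 2 | 45% | 36% |
| Lognormal, sigma 0.5 | 48% | 39% |
| Exponential | 52% | 36% |
| Lognormal, sigma 1 | 73% | 56% |

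The range is 25% to 73%. Starting from 80% power, the ends give Φ(2.802 × √0.75 − 1.960) = 68% and Φ(2.802 × √0.269 − 1.960) = 31%. A less favourable cut can lose more: the most skewed shape cut at its 30th percentile loses 85%.

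The scale of the gradient matters. If intake is lognormal but the label effect is linear in log intake, the normal row applies and a median cut loses 36%.

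**The case against.** The strongest case on the other side has five parts.

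- **The analysis is exploratory and the SAP does not contain it.** This stands. The SAP's primary analysis uses two randomised schools, and nothing in it depends on the moderator. A reader might infer that a live, powered test is being undermined. The documents do not support that, because no power is claimed for moderation anywhere.
- **The size is not a document figure.** This stands. A reader might conclude that the plan discards a third of the information. That needs a normal moderator, a median cut and a linear gradient, none of which the plan states.
- **The measure may not be continuous.** This stands in part. The raw items may be ordinal, and the protocol names usual frequency as the moderator, whereas frequency times volume is an amount. But summed frequencies or ordered scores would still carry more than two levels, so a graded measure is a fair inference.
- **A split can be the better test.** This is true if label effects change abruptly at the cut. The squared correlation works in both directions: with a step at the median of a normal moderator, a linear term keeps the same 64%. The documents propose no such threshold.
- **Stating a cut-point in advance would settle the open threshold.** It would, without dropping the two groups, and the documents do not show that the choice of cut would change the answer here. It would not recover the lost information.

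**Conclusion.** The point holds as a minor improvement to the protocol's text. An exploratory moderator that can be graded is reduced to two undefined groups, and using the graded form needs no further data.

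The loss is conditional. With a gradual change in label effect it is about 36% for a normal moderator cut at the median (80% power falling to about 61%), and 25% to 73% across the shapes in the table at a median or upper-quarter cut. These figures rest on an assumed distribution, an assumed cut and a linear gradient, and they ignore clustering.

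It would be tempting to go further and say that the trial's conclusions are weakened, or that graded coding has no drawback. Neither follows. The primary and secondary results do not use this variable, and a graded term brings its own shape assumption and needs a rule for students who report no intake.

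**What to change.** If the moderation analysis is run:

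- Enter usual intake as a graded variable in the arm-by-intake interaction. Use summed frequency or frequency times volume, transformed with a stated rule for zero consumers, or ordered scores if the items prove ordinal. Say which is used.
- Include a check for non-linearity, for example a spline.
- Report estimated label effects at the 25th and 75th percentiles of intake, which serves readers who want a low and a high group.
- If a high/low display is kept, fix the cut before data are re-matched to condition. The SAP's Statistical analysis section already uses that blinding step for data exclusions.

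If the analysis has been dropped, a sentence in the SAP saying so is enough.

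The cost is a model term and a few sentences, with no new data. The downside is small: a shape assumption, and some loss of efficiency if the true effect is a threshold at the cut.
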